## 2. SYNOPSIS

Name of Sponsor/Company: Santen Incorporated [name]	
Name of Investigational Product: DE-109 injectable solution	
Name of Active Ingredient: Sirolimus	
Title of Study: A Phase IIIb, Multinational, Multicenter, Open-Label Extension Study Assessing the Long-Term Safety of PRN Intravitreal Injections of DE-109 in Subjects with Non-Infectious Uveitis of the Posterior Segment of the Eye Who Have Participated in the SAKURA Development Program	
Study Period (years): Estimated date first subject enrolled: August 2014 Estimated date last subject completed: November 2017	Phase of Development: Phase IIIb Safety Study
Objective: The objective of this extension study is to evaluate the long-term safety of treatment with DE-109 (440 µg) in subjects with non-infectious uveitis of the posterior segment of the eye who have participated in the SAKURA development program.	
Methodology: This is a multicenter, open-label, extension study of intravitreal injections of the 440 µg dose of DE-109 in subjects with non-infectious uveitis of the posterior segment who received any dose of DE-109 and exited the SAKURA program under Santen Protocol 32-007, Amendment 05.  Subjects who were randomized and received at least two injections of DE-109 during the first five months of the SAKURA program and obtained clinical benefit from the study medication, as determined by the Investigator, may be considered for entry in this 12-month extension study. The minimum time lag from last injection in the SAKURA program to entry into the current protocol is 60 days.  The study eye to be treated in this extension study will be the same as the eye treated during the SAKURA program.  Study assessments will be conducted for all subjects at Day 1 (Baseline) and Month 12. Each subject will be followed according to the Investigator's standard clinical practice at non-study visits. DE-109 treatment may be administered in the study eye at the Investigator's discretion during the 12-month study period but no more frequently than every 60 days.  If the Investigator administers a DE-109 injection to the subject, the visit will be considered a Post-Baseline PRN Treatment Visit and procedures will be performed and recorded as specified in this protocol.  All subjects will exit the study at Month 12, unless terminated early. Adverse events will be recorded and collected throughout this extension study, up to the Month 12 exit visit.	
Administration of DE-109: 
 
• The study eye will be the eye treated in the SAKURA program.
 
• DE-109 should NOT be administered to the fellow eye.
 
 Rescue therapy: During the study, rescue therapy may be used at the discretion of the Investigator.	

**Masking:** This is an open-label extension study. All subjects in this unmasked study will receive the 440 µg dose of DE-109.

**Number of Subjects (planned):** The number of subjects to be enrolled in the study will be approximately 200.

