### **9.3.      Treatment Compliance**

The Investigator is not required to administer DE-109 at any visit. DE-109 treatments may be given, as needed, at the discretion of the Investigator; however, DE-109 treatments may not be given more frequently than every 60 days.

The Investigator is responsible for scheduling the subject for follow-up visits based on the Investigator's standard clinical procedures and these visits are not study visits. If a subject receives treatment with DE-109 (440  $\mu$ g) between scheduled study assessments, the visit will be a Post-Baseline PRN Treatment Visit and procedures will be performed and recorded as specified in this protocol (See [Table 3](#)).

Study monitors will verify pertinent data to confirm the study is conducted according to the protocol.

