## 4.5. Other Definitions

### 4.5.1. Rescue Therapy and Rescue Rate

*Rescue therapy* refers to any treatment that would have a therapeutic effect on the uveitis in the posterior segment (e.g., systemic treatment with an immunosuppressant agent, or a corticosteroid injection in the study eye) other than intravitreal DE-109. Topical ocular corticosteroid medication is not considered rescue therapy. Data related to rescue therapies will be reviewed and documented by the Medical Monitor prior to database lock to make the final determination of whether a medication will be classified as rescue therapy. *Rescue rate* is defined as the percentage of subjects who receive rescue therapy during the SPRING study among all subjects.

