### **8.7. Use of Rescue Therapy**

Subjects who take any medication qualified as rescue therapy, or who have vitrectomy procedures in study eye will be listed. The rescue rate in SPRING study will be calculated. Time to first rescue from Day 1 for rescued subjects will be summarized descriptively. Subgroup analysis of rescue rate will be performed by rescue status in SAKURA study, and received injection or not in SPRING study.

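### SAP 8.7 splits the rescue rate by whether DE-109 was ever injected in SPRING, a grouping that the rescue decisions help to form, so the split can differ with no drug effect

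*Protocol*

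**What the plan says.** **Treatment rules.** The Protocol Synopsis says of rescue: "During the study, rescue therapy may be used at the discretion of the Investigator". Section 9.2.2 repeats this and adds no criteria. DE-109 "may be administered in the study eye at the Investigator's discretion during the 12-month study period but no more frequently than every 60 days", and Protocol 9.3 adds: "The Investigator is not required to administer DE-109 at any visit". A subject can therefore finish with no injection, and SAP 7.6 lists zero as an exposure category.

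**Definition of rescue.** SAP 4.5.1 says that rescue "refers to any treatment that would have a therapeutic effect on the uveitis in the posterior segment" and is "other than intravitreal DE-109". Topical ocular corticosteroid is left out. The rescue rate "is defined as the percentage of subjects who receive rescue therapy during the SPRING study among all subjects".

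**The split.** SAP 8.7 (listed as 8.6 in the SAP's table of contents) says: "Subgroup analysis of rescue rate will be performed by rescue status in SAKURA study, and received injection or not in SPRING study". Time to first rescue is measured from Day 1. The SAP gives no rule on the order of rescue and injection, and no caution on reading the split.

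**Status.** SAP 6.1 plans no inferential analysis. SAP 3.3 puts enrolment at 60.

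**The concern.** DE-109 and rescue are two discretionary treatments for the same uveitis. Whether a subject is ever injected is settled during follow-up, partly by the decisions that also produce rescue. Three things follow.

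- A subject given rescue in place of DE-109 may stay in the never-injected row, which raises the rescue rate there.
- A subject with more disease activity has more occasions for both treatments, which raises the rescue rate in the injected row.
- A subject rescued first and injected later counts as rescued in the injected row, although the rescue came before any SPRING exposure.

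Full 12-month follow-up of every subject would remove none of these. Rescue is a listed safety parameter, and this is its only planned split by SPRING exposure. A gap between the rows could be taken as a statement about DE-109 that the table cannot support.

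**Working it through.** The plan states no rescue rate, power or effect size, so there is no figure to reproduce. The question is whether the split can differ when DE-109 does nothing. Every rate below is an assumption. *Flare* is shorthand for an episode of disease activity that prompts treatment; the documents do not use it as a treatment trigger. Flares are independent of treatment throughout, so the true drug effect is zero.

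**1. Three cases that can be checked by hand.** DE-109 is chosen at a flare with probability 0.7, otherwise rescue.

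- *At most one flare, probability 0.7.* Injected: 0.7 × 0.7 = 0.49, none of them rescued, so 0%. Never injected: 1 - 0.49 = 0.51, of whom 0.7 × 0.3 = 0.21 are rescued. 0.21 / 0.51 = 41%. Difference -41 points.
- *Poisson flares, mean 1.5, same for everyone.* Injections and rescues are then independent streams, and both rows give 1 - exp(-1.5 × 0.3) = 1 - exp(-0.45) = 36%. Difference zero.
- *Mean 1.5, with flare rates varying between subjects (gamma, shape 1).* P(never injected) = 1 / (1 + 1.05) = 0.488. P(neither treatment) = 1 / (1 + 1.5) = 0.400. Rescue among the never injected = 1 - 0.400 / 0.488 = 18%. P(rescued) = 1 - 1 / (1 + 0.45) = 0.310. Rescue among the injected = (0.310 - 0.088) / 0.512 = 43%. Difference +25 points.

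One null thus gives a negative, a zero and a positive difference.

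**2. A 12-month simulation in monthly steps.** Inputs: flare hazard 0.15 per month, 30% injected on Day 1, DE-109 chosen at 70% of flares. *Displacement* means that a first rescue ends all later DE-109.

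| Assumption | Rescued, injected | Rescued, never injected | Difference (points) |
|---|---|---|---|
| Displacement, identical flare rates | 32% | 60% | -28 |
| Displacement, varying flare rates | 33% | 35% | -2 |
| No displacement, identical flare rates | 39% | 43% | -4 |
| No displacement, varying flare rates | 39% | 20% | +19 |

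The first row can be checked directly.

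- P(no flare in 12 months) = exp(-1.8) = 0.165.
- Among those not injected on Day 1, P(first flare met with rescue) = 0.3 × 0.835 = 0.250.
- Never injected: 0.250 / (0.250 + 0.165) = 60%.
- Monthly flare probability: 1 - exp(-0.15) = 0.139. P(rescued) overall = 1 - (1 - 0.3 × 0.139)^12 = 0.401.
- Injected: (0.401 - 0.7 × 0.250) / 0.709 = 32%, where 0.709 = 1 - 0.7 × 0.416 is the injected share.

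In the last row of the table, about 26% of subjects who were both rescued and injected had their first rescue before any SPRING injection. Adding an approximate 60-day minimum interval to that row gives 48% versus 20%, because soon after an injection rescue is available and DE-109 is not.

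**3. Would rates per subject-month cure it?** First rescues per 100 subject-months, before versus after the first SPRING injection, under the same null:

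- varying flare rates, no displacement: 2.7 versus 4.1;
- the same with a two-month lockout for the 60-day rule: 2.7 versus 6.0;
- identical flare rates with the lockout: 4.2 versus 6.3.

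This measure assigns each rescue to the right period, but it is still confounded by disease activity and by the minimum interval.

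**The case against.** The best defence is that nothing is tested, efficacy is not the main objective, and no passage reads the split as a drug effect. SAP 8.1 uses the same injected-or-not layer in all adverse event tables, so it is a routine descriptive cut. SAP 8.7 already lists rescued subjects, SAP 8.6 summarises time to first injection and SAP 7.5 lists medication dates, so a careful reader could probably recover the order. With 60 subjects the table is also imprecise. If 45 were injected, 15 were not and 35% were rescued (all assumed), the 95% half-width is 1.96 × √(0.35 × 0.65 × (1/45 + 1/15)) = 28 points.

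Most of this stands, and it limits the harm to interpretation. It does not justify placing pre-injection rescues in the injected row when the dates to avoid this are collected.

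A reader might also infer three stronger things that the documents do not support.

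- *The split is known to be biased by 28 or 19 points.* Those figures come from opposite corners of the assumptions. The other two combinations nearly cancel, and no passage says that a rescue ends later DE-109.
- *DE-109 and rescue are mutually exclusive.* No passage says so, and both may be given.
- *Error rates are affected.* No test is planned.

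**Conclusion.** The point holds as a matter of interpretation. The injected-or-not grouping in SAP 8.7 is formed after baseline, partly by the decisions that produce rescue, and it credits pre-injection rescues to the injected row. With no drug effect the difference between the rows can run from about -28 to +19 points under one set of assumed inputs. More extreme assumed settings go further both ways (0% versus 54%, and 68% versus 14%), and some give nearly nothing. Size and sign depend on how flare rates vary, how investigators choose and how the 60-day interval bites, none of which the documents quantify. The split therefore cannot support a statement about DE-109 in either direction.

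The overall rescue rate is unaffected. So is the split by SAKURA rescue status, which is fixed before entry.

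**What to change.** In SAP 8.7, replace the split by injection received or not with a classification of each subject by dates already collected:

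1. first rescue before any SPRING injection, including subjects rescued and never injected;
2. first rescue after at least one SPRING injection, with days since the last injection;
3. not rescued.

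Add a sentence that the table does not estimate a DE-109 effect, because treatment follows disease activity. State how a first rescue on the same date as the first injection is classified. Mark any classification that rests on an imputed start date, since SAP 6.2.2 imputes partial start dates to the first day of the month or year and so moves rescue earlier.

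Do not present before-and-after rates per subject-month as an unbiased replacement. If they are shown, they need the same caution. Keep the split by SAKURA rescue status.

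The cost is SAP wording, one reprogrammed table and a less simple percentage. No new data are needed and no clinical rule changes.

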### **Diagnosis and Main Criteria for Inclusion:**

#### **Inclusion Criteria:**

At Day 1, a subject from the SAKURA program must meet all of the following inclusion criteria:

1. Have a subject number from participation in the SAKURA program
2. Exited the SAKURA program under Amendment 05
3. Have received at least two injections of DE-109 in the first five months of the SAKURA program
4. Received clinical benefit from treatment with DE-109 as determined by the Investigator
5. Female participants of childbearing potential must not be pregnant or breast-feeding, have a negative pregnancy test at Day 1 and must be willing to undergo pregnancy tests throughout the study
6. Both female participants of childbearing potential and male participants able to father children must have (or have a partner who has) had a hysterectomy or vasectomy, must abstain from intercourse or must agree to practice acceptable methods of contraception throughout the course of the study
7. Ability to give informed consent and attend all study visits

#### **Exclusion Criteria:**

A subject from the SAKURA program with any of the following conditions is not eligible to participate in the study:

##### **Ocular:**

1. Active infectious uveitis. However, if the uveitis is the consequence of a previous infectious disease, such as tuberculosis, the previous infectious disease must be confirmed as no longer active.
2. Any implantable corticosteroid-eluting device (e.g. Ozurdex, I-vation, Iluvien, fluocinolone acetonide [FA] intravitreal implant) in the study eye:
  - a. If the Investigator confirms the device has no demonstrable efficacy as indicated in the package insert, the subject will be eligible
  - b. If a Medidur implant, Iluvien or Retisert has been implanted no less than 3 years and 90 days prior to Day 1, the subject will be eligible
  - c. If a Ozurdex implant has been implanted no less than 180 days prior to Day 1, the subject will be eligible
3. Clinically suspected or confirmed central nervous system or ocular lymphoma
4. Progressive glaucoma which is unresponsive to treatment.
5. Intraocular pressure of > 21 mmHg while on medical therapy, or chronic hypotony (< 6 mmHg)
6. Any significant ocular disease that could compromise vision in the study eye. These include, but are not limited to:
  - a. Diabetic retinopathy: proliferative diabetic retinopathy (PDR) or non-proliferative diabetic retinopathy (NPDR) that compromises vision. Subjects with NPDR or PDR

that does not compromise vision are not excluded from the study;

- b. Wet age-related macular degeneration;
- c. Myopic degeneration with active subfoveal choroidal neovascularization

7. Any of the following treatments to the study eye:
  - a. Intravitreal injections in the past 14 days
  - b. Intravitreal injections of DE-109 in the past 60 days
8. Ocular surgery within the past 30 days
9. Ocular or periocular infection in either eye
10. History of or active herpetic infection in the study eye or adnexa
11. Presence of known active, inactive toxoplasmosis or toxoplasmosis scar in either eye
12. Presence of any form of ocular malignancy in the either eye including choroidal melanoma
13. History of vitrectomy in the study eye

Non-Ocular:

14. Allergy or hypersensitivity to study drug product or other study related procedures/medications
15. Participation in other investigational drug (SAKURA is an exception) or device clinical trials within 30 days prior to Day 1, or planning to participate in other investigational drug or device clinical trials for the entire duration of the study. This includes both ocular and non-ocular clinical trials.
16. Any recent systemic infection within 30 days of Day 1
17. Known to be immunocompromised
18. History of cytomegalovirus infection or clinical evidence of active cytomegalovirus infection at Day 1
19. History of other disease, metabolic dysfunction, physical examination finding, or clinical laboratory finding giving reasonable suspicion of a disease condition that contraindicates the use of an investigational drug, might affect the interpretation of the results of the study, or renders the subject at high risk for treatment complications
20. Malignancy in remission for less than 5 years prior to study participation (except basal cell or squamous cell skin cancer, or treated melanoma of the skin less than 24 months since last treatment)
21. Females who are pregnant or lactating and females of child-bearing potential who are not using adequate contraceptive precautions (i.e., intrauterine device, oral contraceptives, barrier method, or other contraception deemed adequate by the Investigator)
22. Use of medically prescribed marijuana or other illegal medication
23. Active systemic sarcoidosis within the last 30 months (i.e. subjects with uveitis secondary to sarcoidosis will be eligible as long as systemic sarcoidosis is not active and systemic immunosuppressive therapy has not been given in the last 30 months)
24. Therapeutic radiation to the head or neck within 90 days prior to Day 1 and throughout the study

In addition, the Investigator or Santen Medical Monitor may declare a subject ineligible for any sound reason.

**Investigational product, dosage and mode of administration:**

Investigational product: DE-109 injectable solution, 440 µg.

Subjects will be treated at the discretion of the Investigator, but no more frequently than every 60 days.

Route of Administration: 20 $\mu$ L intravitreal injection in the study eye.
Duration of the Study: 12 months or commercial availability of DE-109, whichever comes first.
Criteria for Evaluation:
Safety: The long-term safety of DE-109 440 $\mu$ g will be assessed based on adverse events, visual acuity, intraocular pressure, indirect ophthalmoscopy variables, vitreous haze and the use of rescue therapy.
Efficacy: Efficacy is not the main objective of this extension study. The long-term efficacy of DE-109 440 $\mu$ g may be explored by vitreous haze.
Safety Parameters: 

• Adverse event incidence rate

• Change in best-corrected visual acuity

• Change in intraocular pressure

• Change in indirect ophthalmoscopy findings

• Change in vitreous haze

• Proportion of safety subjects who were rescued

Statistical Methods: 
This extension study is implemented to provide subjects with access to DE-109 to benefit those who have received at least two injections of DE-109 during the first 5-month treatment of the SAKURA development program and to evaluate the long-term safety of DE-109 440 <math>\mu</math>g in subjects with non-infectious uveitis of the posterior segment of the eye.
 
No statistical hypotheses will be tested in this study.
 
The safety data will be summarized descriptively. The Safety population will include all enrolled subjects with any safety data collected during the study, whether or not they ever receive any injection of DE-109 (440 <math>\mu</math>g). It will be the analysis population for safety summaries.
 
The formal definition of rescue therapy will be adequately documented based on clinical data review of this extension study prior to database lock.

#### 4. LIST OF ABBREVIATIONS AND DEFINITIONS OF TERMS

The following abbreviations and specialist terms are used in this study protocol.

**Table 2: Abbreviations and Specialist Terms**

Abbreviation/Term	Definition
AE	Adverse Event
Baseline	Earliest Assessment of Each Measure on Day 1
BCVA	Best-Corrected Visual Acuity
DE-109	Sirolimus Injectable Solution
eCRF	Electronic Case Report Form
ETDRS	Early Treatment of Diabetic Retinopathy Study
FDA	Food and Drug Administration
FKBP-12	FK binding protein 12
EDC	Electronic Data Capture
GCP	Good Clinical Practice
ICH	International Conference on Harmonization
IEC	Independent Ethics Committee
IL	Interleukin
IOP	Intraocular Pressure
IRB	Institutional Review Board
MedDRA	Medical Dictionary for Regulatory Activities
MHC	Major Histocompatibility Complex
mTOR	Mammalian Target of Rapamycin
NEI	National Eye Institute
NPDR	Non-Proliferative Diabetic Retinopathy
PDR	Proliferative Diabetic Retinopathy
SAE	Serious Adverse Event
SAKURA	Santen Protocol 32-007
SAP	Statistical Analysis Plan
SAS	Statistical Analysis Software
SUN	Standardized Uveitis Nomenclature Photographic Scale
USA	United States of America
VH	Vitreous Haze

## 5. INTRODUCTION

Uveitis is a heterogenous group of intraocular inflammation disorders with both exogenous (infection, trauma) and endogenous (autoimmune disorders, idiopathic) etiologies. The most widely used classification of uveitis is based on the anatomical location of the inflammation within the eye. Anterior uveitis is the most common type and can involve the cornea, iris, and/or ciliary body. Intermediate uveitis affects the middle portion of the eye, such as the ciliary body, anterior vitreous and peripheral retina. Posterior uveitis can involve the vitreous, choroid, retina, and/or optic nerve. Panuveitis, also referred to as diffuse, involves the anterior and posterior segments.

Uveitis is responsible for approximately 10% of the visual handicap in Western countries ([Nussenblatt, 1990](#)). The prevalence of posterior uveitis and its associated ocular morbidity is not well characterized. However, one study of an Israeli population and another of a Netherlands population approximated that 15 to 22% of uveitis affect the posterior segment ([Rothova et al., 1996](#); [Weiner et al., 1991](#)), while the study of Veterans Affairs patients estimated 10% with posterior uveitis ([Suhler et al., 2008](#)). The study of the Netherlands population also found that in patients with posterior uveitis, 46% experienced visual loss of <20/40 or greater and 28% experienced macular edema ([Rothova et al., 1996](#)). In chronic uveitis, cumulative structural damage and loss of vision result from recurrent episodes of inflammation. T-cell infiltration is primarily responsible for the inflammation ([Barton et al., 1995](#)). T-cells release cytokines including various interleukins (IL-2, IL-4, and IL-10) and interferon gamma ([Barton et al., 1995](#)). Major histocompatibility complex molecules (MHC Class I and II) and adhesion molecules are upregulated by the cytokine release ([Charteris et al., 1992](#); [George et al., 1997](#); [Whitcup et al., 1992a](#)). In experimental uveitis models, adhesion molecules have been found on ocular resident cells before leukocytes reach the inside of the eye ([Whitcup et al., 1993](#); [Whitcup et al., 1992b](#)). Thus, adhesion molecules enable leukocytes to migrate to the site of inflammation, contributing to the inflammatory cascade that occurs with active uveitis.

Corticosteroids are the mainstay of treatment for active, non-infectious uveitis. Corticosteroids are administered topically, by periocular injection, via intravitreal injection and implant, or systemically. Topical corticosteroids are useful for the management of anterior uveitis. In general, periocular corticosteroid injections are appropriate for intermediate uveitis. Retisert™ is a fluocinolone acetonide intravitreal implant which releases drug slowly over a period of months. This product was approved by the Food and Drug Administration (FDA) in 2005 for the treatment of chronic non-infectious uveitis affecting the posterior segment of the eye. Long-term data shows that subjects who receive fluocinolone acetonide implants sometimes require cataract extraction and a significant percentage require treatment to reduce IOP ([Callanan et al., 2008](#)). Even though this newer treatment approach is now available, many patients with chronic, posterior uveitis are more difficult to manage and require systemic corticosteroids due to recurring inflammation. Co-morbidities from systemic corticosteroid use are well known, such as Cushingoid syndrome, diabetes, osteoporotic bones, and metabolic disturbances ([Anglade et al., 2007](#)). Systemic immunosuppressive agents, although they require close monitoring, are therefore sometimes utilized for their steroid-sparing capabilities. Immunosuppressive agents can be categorized into three (3) main classes: T-cell inhibitors (cyclosporine, tacrolimus), antimetabolites (azathioprine, methotrexate, mycophenolate mofetil, leflunomide), and alkylating

agents (cyclophosphamide, chlorambucil). More recently, biologic agents have been explored for use in uveitis, including tumor necrosis factor- $\alpha$  inhibitors (infliximab, etanercept, and adalimumab), anti-lymphocyte agents (rituximab and alemtuzumab), and an interleukin-2 receptor blocker (daclizumab).

Currently corticosteroids are the only approved drug class in the United States for non-infectious uveitis. Systemic cyclosporine which blocks T-cell activation and inhibits the production of cytokines has been approved in Germany and a few other countries for treatment-refractory uveitis but is not approved in the United States. Although a variety of treatment options are available, the co-morbidities associated with corticosteroids and the inconvenience of close monitoring required with systemic immunosuppressive and biologic agents warrant more treatment options.

Sirolimus for ocular administration is being tested with a proprietary formulation, DE-109 for the treatment of non-infectious, posterior uveitis. This proprietary formulation was originally developed by MacuSight, Inc. and in June 2010, Santen, Inc. acquired the worldwide rights to the formulation. The formulation provides drug exposure to the retina/choroid for up to approximately 2 months, and is amenable to delivery by the intravitreal route of administration. The active pharmaceutical ingredient in the formulation is sirolimus. Sirolimus, also known as rapamycin, was isolated in the 1970's from *Streptomyces hygroscopicus* in soil samples from Easter Island (Napoli et al., 2001). Sirolimus is the active pharmaceutical ingredient in 2 products approved by the FDA, specifically Rapamune®, an immunosuppressive agent used in renal transplant patients, and the CYPHER® sirolimus-eluting Coronary Stent approved for improving coronary luminal diameter in patients with symptomatic ischemic disease.

The mechanism of action of sirolimus in immunoregulation has been described extensively in the literature (Kahan, 2001; Napoli et al., 2001; Sehgal, 1998; Sehgal, 2003). Sirolimus blocks T-lymphocyte activation and smooth muscle and endothelial cell proliferation that occurs in response to antigenic and cytokine (IL-2, IL-4 and IL-15) stimulation employing either Ca2+-dependent or Ca2+-independent pathways (Rapamune, 2009; Sehgal, 1995; Sehgal, 1998). Sirolimus arrests cell cycle progression by direct interaction with 2 intracellular proteins, specifically the immunophilin FK binding protein 12 (FKBP-12) and the mammalian target of rapamycin (mTOR), a multifunctional serine-threonine kinase (Napoli et al., 2001). In cells, sirolimus binds to FKBP-12, and the resulting sirolimus: FKBP-12 complex then binds to and inhibits mTOR. The inhibition of mTOR blocks IL-2 mediated signal transduction pathways that prevent cell cycle progression from G1 to S phase in T cells, endothelial cells, osteosarcoma cells, myogenic cell lines and smooth muscle cells (Kwon et al., 2005; Sehgal, 1998). In addition, sirolimus inhibits the production of antibodies (Sehgal, 1995; Sehgal, 1998). Sirolimus has also been shown to down-regulate the expression of many genes related to inflammation such as interleukin-8, endothelial-monocyte activating polypeptide II, granulocyte chemotactic protein 2, cyclooxygenase 1 and 2, and inducible nitric oxide synthase (Adamis, 2002; Attur et al., 2000; Joussen et al., 2004; Nuhrenberg et al., 2005).

Similar to cyclosporine, sirolimus blocks T-cell activation and inhibits the production of inflammatory cytokines. Moreover, tacrolimus, another immunomodulatory agent closely related to sirolimus, has shown effectiveness in uveitis refractory to cyclosporine (Kilmartin et al., 1998; Sloper et al., 1999). Since sirolimus provides an inhibitory effect on inflammation, it may be beneficial in the treatment of active, non-infectious uveitis.

Sirolimus has been administered to patients with non-infectious intermediate, posterior uveitis, or panuveitis in an investigator-sponsored protocol trial known as the SAVE study ([Nguyen et al., 2013](#)). This was an initial Phase I study evaluating intravitreal and subconjunctival administration of sirolimus and the results of the study supported the continued development of DE-109.

The SAKURA development program is a multinational, multicenter, randomized, double-masked protocol (Santen Protocol 32-007) assessing the safety and efficacy of three doses of DE-109 (44 µg, 440 µg and 880 µg) administered every 2 months in subjects with active, non-infectious uveitis of the posterior segment of the eye. A planned unmasked analysis of 6-month data of 347 subjects has been completed. In the analysis, both the 440 µg and 880 µg doses of DE-109 demonstrated efficacy in the treatment of non-infectious uveitis affecting the posterior segment of the eye. The 440 µg dose demonstrated statistically significant differences for the primary and key secondary endpoints when compared to the 44 µg dose. Efficacy results for the 880 µg dose regimen were not as significant compared to the 44 µg dose. Additionally, there was a tendency towards increased reporting of AEs associated with intraocular inflammation following intravitreal administration with the 880 µg dose. In the overall analysis, the 440 µg dose demonstrated a more favorable Benefit-Risk profile than the 880 µg dose. The SAKURA development program is on-going and continues to enroll.

This study (Santen, Protocol 32-009) is being initiated to allow subjects continued access to DE-109 (440 µg) following participation in the SAKURA program and to obtain additional long-term safety data on the to be developed dose.

